### 3.0 TRIAL DESIGN

#### 3.1 Objectives

The primary objective is to determine the tolerability of LOAd703 given by i.t. injection(s) in combination with atezolizumab administered by IV.

The secondary objectives are to determine the antitumor activity as well as the pharmacokinetics and biological mechanisms-of-action of LOAd703 in combination with atezolizumab.

#### 3.2 Endpoints

##### Primary Endpoints

- 1) The primary endpoint is safety, determined by the National Cancer Institute Common Toxicity Criteria for Adverse Events (NCI CTCAE) v5.0.

##### Secondary Endpoints

- Overall response rate evaluated by RECIST v1.1.
- Sheding determined as level of LOAd703 [REDACTED]
- LOAd703 leakage to blood [REDACTED]
- Anti-adenovirus immunity [REDACTED]
- [REDACTED]
- [REDACTED]
- Immune profile as [REDACTED]
- [REDACTED]

#### 3.3 Summary of Trial Design

This trial is a multicenter, open label, single arm, dose-escalation Phase I/II trial. The study will have a Bayesian Optimal Interval (BOIN) design (target DLT rate=0.3) to determine the MTD of LOAd703 against a fixed dose of atezolizumab. This design has algorithmic escalation/de-escalation rules like a traditional 3+3 design, but it also allows for specification of the target DLT rate and expanded accrual beyond N=6 with continued and consistent toxicity monitoring. This means that the assessment of DLT rate continues throughout the study, giving a well-defined safety evaluation of the entire study. Refer also to sections *10.0 STATISTICS*, *5.5 Dose Limiting Toxicity (DLT)* and *5.6.9 LOAd703 Maximum Tolerated Dose (MTD)*.

[REDACTED]  
The total number of patients to be enrolled in the study to achieve at least 25 evaluable patients at MTD, should not exceed 50.

### 3.4 Duration of Study

Timeline:	First patient in	Q3 2020
	Last patient's last visit	Q1 2024
	Study end	Q12024

After a screening period [REDACTED], each patient will receive a maximum of 12 LOAd703 injections (q3w) in combination with atezolizumab (q3w) after which supportive therapy with atezolizumab alone is continued until the final clinical visits (i.e. maximum 7 additional infusions). The patients will be scheduled for study visits until final clinical follow-up in study [REDACTED]

If both treatments are prematurely discontinued the final clinical follow-up visit could be scheduled earlier, [REDACTED]

In total, patients will visit the clinic regularly for a maximum 60-weeks ([REDACTED]). Thereafter only OS will be recorded every [REDACTED] whereby information will be collected via e.g. telephone calls (US) or medical records (SWE, US) until death or study end.

### 3.5 End of Study

The End of the treatment stage is defined as the date of the LPLV and the End of study is defined as LPLV.

## 4.0 SELECTION AND WITHDRAWAL OF PATIENTS

Study patients will be recruited among patients taken care of at the study center but may also include patients referred from other hospitals. Once a patient is enrolled in the trial, the Site Investigator is responsible for the care of the patient.

Patients must meet all the following inclusion criteria and none of the exclusion criteria to be registered in the study:

### 4.1 Inclusion Criteria

1. Pathological confirmation of melanoma.
2. A life expectancy of at least 3 months as per the investigator.
3. **Valid for Swedish patients:** Patients has locally advanced melanoma or metastatic melanoma, but not eligible for complete resection of melanoma.  
**Valid for US patients:** Patients has locally advanced melanoma or metastatic melanoma.
4. The patient has measurable disease (e.g., measurable tumor lesions must be present that can accurately be measured in at least one dimension with a minimum size of 10 mm by CT scan and MRI, 10 mm caliper measurement by clinical exam (when superficial), and/or 20 mm by chest X-ray).

5. Patient has at least one injectable tumor lesion that has not been irradiated or has been irradiated but disease progression documented at the site subsequent to radiation therapy.
6. The patient has received appropriate treatment with an anti-PD-1 or anti-PD-L1 antibody with or without an anti-CTLA4.
7. **Valid for Swedish patients:** Patients whose advanced melanoma has a B-Raf mutation must have received appropriate therapy with tyrosine kinase inhibitor(s) and/or MEK inhibitor  
**Valid for US patients:** Patients whose advanced melanoma has a B-Raf mutation may have received appropriate therapy with tyrosine kinase inhibitor(s) and/or MEK inhibitor as assessed by the investigator.
8. Age  $\geq$  18 years.
9. Eastern Cooperative Oncology Group (ECOG) performance status of 0 to 1.
10. Serum albumin  $\geq$  2.5 g/dL.
11. Absolute neutrophil count (ANC)  $\geq$  1.0  $\times$  10e9/L.
12. Platelet count  $\geq$  100  $\times$  10e9/L.
13. Prothrombin (INR)  $\leq$  1.5 or prothrombin time (PT)  $\leq$  1.5 times ULN; and either partial thromboplastin time or activated partial thromboplastin time (PTT or aPTT)  $\leq$  1.5 times the ULN.
14. Bilirubin  $<$  1.5 times the institutional upper limit of normal (ULN).
15. Aspartate aminotransferase (AST) and alanine aminotransferase (ALT)  $\leq$  2.5 ( $\leq$  5 if liver metastases are present) times the institutional ULN.
16. The patient must have signed informed consent.

#### 4.2 Exclusion Criteria

1. Malignant melanoma that is uveal.
2. Subjects considered by the investigator to have rapid clinical progression due to melanoma.
3. Subjects must not have greater than 3 cerebral melanoma metastases, and/or clinically active cerebral melanoma metastases, and/or a requirement for corticosteroid therapy, and/or carcinomatous meningitis regardless of clinical stability.
4. Any concurrent treatment that would interfere with the effect mechanisms of atezolizumab and LOAd703, including, but not limited to, continuous high-dose corticosteroids ( $>10$  mg per day), lymphodepleting antibodies, or cytotoxic agents.
5. Treatment with inhibitors of immune function, such as lymphotoxic monoclonal antibodies (e.g., alemtuzumab), or rapamycin/rapamycin analogs, or cytotoxic agents within 21 days of the first dose of LOAd703/atezolizumab.
6. Therapeutic treatment with systemic antibiotics within 14 days of the first dose of LOAd703/atezolizumab.
7. Treatment with biologic therapy within 21 days of the first dose of LOAd703/atezolizumab.
8. Treatment with cytotoxic anticancer therapy within 14 days of the first dose of LOAd703/atezolizumab.
9. Treatment with wide-field radiation within 14 days of the first dose of LOAd703/atezolizumab.
10. Prior treatment with an adenovirus-based gene therapy.
11. Use of any investigational agents within 21 days of the first dose of LOAd703/atezolizumab.
12. The use of systemic immunostimulatory agents (including, but not limited to, interferons and IL2) are prohibited within 21 days or 5 half-lives (whichever is longer) of the first dose of LOAd703/atezolizumab.

13. Failed resolution/improvement of AEs including those related to anti-PD-1/anti-PD-L1 to grade 0-1 and requirement for treatment with  $\geq 10$  mg/day prednisone (or equivalent) for at least two weeks prior to registration.
14. History of CTCAE grade 4 immune-related AEs from monotherapy using an anti-PD-1/anti-PD-L1 antibody.
15. History of CTCAE grade 4 AE that require steroid treatment ( $>10$  mg/day prednisone or equivalent) for  $>12$  weeks.
16. Patients requiring warfarin are not eligible (low molecular weight heparin is permitted).
17. Women who are pregnant (as confirmed by pregnancy test during screening in applicable patients), breastfeeding, or planning to become pregnant during the study period, or women of childbearing potential who are not using acceptable highly effective contraceptive methods. A woman is considered of childbearing potential if she is not surgically sterile or is less than 1 year since her last menstrual period. The following are acceptable as highly effective contraceptive methods: combined (estrogen- and progesterone-containing) hormonal contraception associated with inhibition of ovulation (oral, intravaginal, transdermal), progesterone-only hormonal contraception associated with inhibition of ovulation (oral, injectable, implantable), intrauterine device, intrauterine hormone-releasing system, bilateral tubal occlusion and vasectomized partner or abstinence of heterosexual intercourse during the entire study period (depending on the preferred and usual life style of the subject).
18. Men who do not consent to the use of condoms during intercourse during study participation or has a partner of childbearing potential, who will not use any of the highly effective contraceptive methods exemplified in exclusion criteria no 17.
19. Known active hepatitis B or C infection, or HIV infection.
20. Patients with active, severe autoimmune disease or immune deficiency or previous Guillain-Barré syndrome. Patients with eczema, psoriasis, lichen simplex chronicus or vitiligo with dermatologic manifestations only (e.g., patients with psoriatic arthritis are excluded) are eligible for the study provided all of following conditions are met:
  - a. Rash must cover  $<10\%$  of body surface area.
  - b. Disease is well-controlled at baseline and requires only low-potency topical corticosteroids.
  - c. Occurrence of acute exacerbations of the underlying condition requiring psoralen plus ultraviolet A radiation, methotrexate, retinoids, biologic agents, oral calcineurin inhibitors, or high-potency or oral corticosteroids within the previous 12 months.
21. History of leptomeningeal disease.
22. Uncontrolled pleural effusion, pericardial effusion, or ascites requiring recurrent drainage procedures (once monthly or more frequently).
23. History of idiopathic pulmonary fibrosis, organizing pneumonia (e.g., bronchiolitis obliterans), drug-induced pneumonitis or idiopathic pneumonitis, or evidence of active pneumonitis on screening chest computed tomography (CT) scan or tested reduced functional respiration capacity. However, history of radiation pneumonitis in the radiation field (fibrosis) is permitted.
24. Unstable angina, uncontrolled cardiac arrhythmia, recent (within 3 months) history of myocardial infarction or stroke, or New York Class III/IV congestive heart failure.
25. Major surgical procedure other than for the malignant melanoma diagnosis, within 4 weeks prior to initiation of the study treatment, or anticipation of the need for a major surgical procedure during the study.
26. Prior allogeneic stem cell or solid organ transplantation.

27. History of severe allergic anaphylactic reactions to chimeric human or humanized antibodies, or fusion proteins.
28. Known hypersensitivity to CHO cell products or any component of the atezolizumab formulation.
29. Uncontrolled intercurrent illness including, but not limited to, psychiatric illness/social situations that in the opinion of the Investigator would compromise compliance to study requirements or put the patient at unacceptable risk.
30. Other malignancy within the past 2 years (not including basal cell or squamous cell carcinoma of the skin, prostate cancer without the need of other treatment than hormones or *in situ* cervix, breast or melanoma).
31. Live, attenuated vaccines (e.g., FluMist®) are prohibited within 4 weeks prior to initiation of study treatment, during treatment, and for 5 months after the final dose of atezolizumab and/or LOAd703.
32. Adenovirus-based vaccines (e.g., Vaxzevria, known as COVID-19 vaccine Astra Zeneca, J&J Covid-19 vaccine) are prohibited 3 months prior to initiation of study treatment, during treatment and 6 months after the final dose of LOAd703.

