#### **7.2.5 Continuation Criteria**

Within -2 days prior to each LOAd703 and/or atezolizumab treatment ([REDACTED]), the Investigator will meet with the patient to confirm that he/she is eligible to continue treatment by reviewing:

- laboratory values
- No AEs/SAEs/DLTs have occurred that require dose reduction or discontinuation of treatment (see sections *5.5 Dose Limiting Toxicity (DLT)*, *5.6.8 LOAd703 Dose Modifications*, and *5.7.7 Atezolizumab Dose Modifications*). Note that additional treatments are not allowed if an ongoing related AE is still grade 3 or higher.
- No withdrawal criteria are fulfilled (see section *4.4 Withdrawal of Patients*).
- ECOG
- The patient is fit to receive another injection, in the opinion of the Investigator.

[REDACTED]

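### Exclusion 20c lacks a negation, so read literally it makes a treated skin flare in the past 12 months a condition of the exception for skin-only autoimmune disease

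*Protocol*

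**What the plan says.** Protocol section 4.0 requires a patient to meet every inclusion criterion and no exclusion criterion. Exclusion 20 opens by barring active, severe autoimmune disease, immune deficiency and previous Guillain-Barré syndrome. It then says that patients with four named skin conditions, with skin manifestations only, "are eligible for the study provided all of following conditions are met". Three items follow:

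- 20a requires a rash on less than 10% of the body surface.
- 20b reads "Disease is well-controlled at baseline and requires only low-potency topical corticosteroids".
- 20c reads "c. Occurrence of acute exacerbations of the underlying condition requiring psoralen plus ultraviolet A radiation, methotrexate, retinoids, biologic agents", then adds oral calcineurin inhibitors and strong or oral steroids, all within the previous 12 months.

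The synopsis and section 4.2 carry the same text. The amendment log describes no change to this item.

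**The concern.** Items a and b must be true for the exception to apply, and both restrict it to mild disease. Item c stands under the same lead-in and is phrased as something that happened. Taken at its word, it makes a flare that needed systemic or high-potency treatment part of qualifying.

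At stake is a safety screen. The trial combines an immunostimulatory virus with a PD-L1 inhibitor, and safety is the primary endpoint. A recent serious flare is the history that a 12-month look-back would be written to catch.

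**Working it through.** No planned figure is involved, so the check is a comparison of texts.

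**1. Direction of the condition.** Take a patient with skin-only disease who satisfies 20a and 20b, and ask whether the exception applies.

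| Flare needing a listed treatment in past 12 months | 20c as written | 20c with *No* in front |
|---|---|---|
| Yes | exception applies | exception does not apply |
| No | exception does not apply | exception applies |

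The two versions disagree in both rows. Items b and c do not formally contradict each other, since b concerns baseline and c the preceding year, but only the negated c points the same way as a and b.

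**2. Extraction fault or later correction?** The same complete sentence appears in two separate places, with no gap or redaction mark, so a PDF fault is unlikely. Nothing visible corrects it. Protocol sections 2.6.2 and 2.6.3 are redacted, section 5.8 is partly redacted, and the site file is not supplied, so a correction there cannot be excluded.

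**3. Does another criterion catch a settled flare?**

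- Exclusion 4 covers concurrent treatment only.
- Exclusion 5 ("Treatment with inhibitors of immune function, such as lymphotoxic monoclonal antibodies (e.g., alemtuzumab), or rapamycin/rapamycin analogs, or cytotoxic agents within 21 days") and exclusion 7 ("Treatment with biologic therapy within 21 days of the first dose of LOAd703/atezolizumab") reach back 21 days. Taking 12 months as 365 days, 365 − 21 = 344 days of the window in 20c lie beyond them.
- Exclusion 13 ("Failed resolution/improvement of AEs including those related to anti-PD-1/anti-PD-L1 to grade 0-1") concerns unresolved events, joined to a steroid requirement.
- Exclusion 14 ("History of CTCAE grade 4 immune-related AEs from monotherapy using an anti-PD-1/anti-PD-L1 antibody") and exclusion 15 have no time limit but cover grade 4 events only.
- Exclusion 29 rests on the investigator's judgment of uncontrolled illness.
- Inclusion 6 means that every patient has already received an anti-PD-1 or anti-PD-L1 antibody. That is relevant history but does not screen for a skin flare.

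Psoralen with UVA, retinoids and high-potency topical steroids are named in no other exclusion. None of these criteria replaces 20c for a flare that has settled.

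**4. Can a correction still reach new patients?** Version 6.1 is dated 9 June 2023, and last patient last visit is planned for Q1 2024. From 9 June 2023 to 31 March 2024 is 296 days. The full visit schedule is 60 × 7 = 420 days, and 420 − 296 = 124. A patient entering at version 6.1 would therefore fall 124 days short of the full schedule by the planned last visit. Earlier final visits are allowed, so later entry is not ruled out. SAP section 6.1 already describes the conduct at four sites in the past tense.

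**The case against.** The strongest reply is that nobody would misread 20c. The list already has to be read by purpose: exclusion 3 says what subjects must not have, although patients must meet none of the exclusions, so taken literally it is inverted too. Exclusions 31 and 32 are phrased as prohibitions. Slots are confirmed by the CRO, and the monitor checks eligibility criteria for every treated patient, so a misapplication had occasions to surface. Most of this stands, and it is why the point is minor. It does not make the text right: 20c is operative and, as worded, points the wrong way.

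Three stronger readings are tempting, and the documents do not support them.

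- *Stable patients are turned away.* A reader might infer this from the second row of the table. But the opening sentence of exclusion 20 bars only active, severe disease. If what follows is a carve-out, failing it does not exclude someone whom the base exclusion never reached. The inference holds only if the lead-in is taken as a requirement in its own right, and the text does not settle that.
- *The protocol has a convention of writing negations out, which 20c breaks.* Section 7.2.5 does include "No AEs/SAEs/DLTs have occurred that require dose reduction or discontinuation of treatment", but that list mixes full conditions with bare items such as laboratory values and ECOG. It does not establish a convention.
- *A patient with a recent flare met the approved text and so cannot be a deviation.* On the literal reading, an enrolled stable patient might then be the one who failed 20c; on the intended reading, it is the patient with the flare. Protocol section 4.6 requires all deviations to be recorded, and protocol section 13.1.2 and SAP section 7.3.2 leave the handling of violations to documented decisions at database closure.

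**Conclusion.** The concern holds as a minor wording error in an operative safety criterion. 20c lacks a negation in both places where it appears. Read literally, it does not screen out a patient with a treated flare in the past 12 months, and no other visible criterion does so once the flare has settled.

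No site is shown to have applied 20c inverted. The number of patients affected is not given and may be zero. Sample size, dose-finding rules and planned analyses are untouched.

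The conclusion assumes that the redacted sections and the site file contain no correction, and that a and b show the intended direction of c.

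**What to change.** In the synopsis and in section 4.2, begin 20c with *No occurrence of* and leave the rest unchanged, by amendment or clarification letter.

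If enrolment is complete, use the screening medical history (protocol section 7.2.3, summarized by preferred term under SAP section 7.4) to find enrolled patients with eczema, psoriasis, lichen simplex chronicus or vitiligo. Check their hospital records for a flare of the kind 20c describes. The concomitant-medication record will not suffice, because protocol section 7.2.12 covers therapies ongoing at screening or given afterwards. Describe any such patient in the study report, and leave the deviation classification to the sponsor's documented database-closure decision.

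The cost is one added word, with the matching change of capital, in two places, a record check confined to those patients, and at most a short note in the report. There is no statistical cost.

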#### **4.3 Screening, Enrollment and Registration Log, Identification List and Numbering of Subjects**

It is the responsibility of the Investigator that all patients considered candidates for the study be listed in the "*Screening, Enrollment and Registration log*". The reason for rejecting a patient before informed consent is obtained should be specified in the comments field of the log. Patients will receive a consecutive patient number when signing the informed consent and are thereafter considered enrolled as study patients so they can initiate the screening visit. The patient number will have the following format: [REDACTED]

[REDACTED] . The trial site will keep an "*Identification list*" of all enrolled patients that connects the subject's identity to their study number.

Study patients who have been screened and excluded before the week 0 visit are considered screening failures and will be noted as such in the "*Screening, Enrollment and Registration log*". The reason for excluding the patient from the study should be specified in the comments field of the "*Screening, Enrollment and Registration log*".

When the inclusion criteria and none of the exclusion criteria have been fulfilled, the site can request a study slot by the CRO. When the study slot is confirmed by the CRO, the patient is considered registered in the study and the registration date is documented in the "*Screening, Enrollment and Registration log*". The study investigators participate in regular phone conferences with the CRO and Sponsor to follow the recruitment process and study development.

**NOTE:** During dose escalation, the slots are limited to 3 per cohort, of which the first patient must receive [REDACTED]

[REDACTED] before patient 2 and 3 can start. During dose escalation it is therefore important to have close communication with the CRO before screening, in order to confirm the timing and avoid having eligible patients ready for treatment when there is no slot available. During dose escalation, the first dose will not be given to two or more patients on the same day (within 24 hours of dosing).

Instructions on communication and the registration procedures are found in the Investigator Site File.

#### 4.4 Withdrawal of Patients

A patient has the right to withdraw his or her consent for participating in the study, at any time, and without giving any specific reason.

The *study treatment* can be discontinued (i.e. from either LOAd703 or atezolizumab or from both treatments) at any time if it is medically necessary, as judged by the Investigator or the Sponsor, based on the development of toxicity as specified in sections *5.5 Dose Limiting Toxicity (DLT)*, *5.6.8 LOAd703 Dose Modifications*, *5.6.9 LOAd703 Maximum Tolerated Dose (MTD)* and *5.7.7 Atezolizumab Dose Modifications*.

If only one of the study treatments is discontinued, the patient still continues with the other study treatment and follows the study schedule according to the protocol.

#### **4.4.1 Off-treatment patient**

The patient is discontinued from both LOAd703 and atezolizumab ( [REDACTED] ) or from Atezolizumab ( [REDACTED] ) if the following criteria are met:

1. The development of toxicity, which precludes further treatment with both study treatments, in the Investigator's judgment, and as specified in sections *5.5 Dose Limiting Toxicity (DLT)*, *5.6.8 LOAd703 Dose Modifications*, *5.6.9 LOAd703 Maximum Tolerated Dose (MTD)* and *5.7.7 Atezolizumab Dose Modifications*.
2. A response that is sufficient to downstage the patient to resectable or borderline resectable disease, in which case the Investigator may decide to pursue chemoradiation and/or surgical resection.
3. Patient has confirmed progressive disease
4. Patient requests to discontinue treatment.
5. Female patient becomes pregnant.

**Off-treatment patients:** should continue to be followed according to a modified clinical follow-up schedule (see section *6.4 Evaluation, Modified Follow-Up and Final Follow-Up Visit* and *14.3 Appendix III: Modified Follow-Up Schedule*). This means that patients will continue his/her participation in the study and return to visits for AE assessment, sampling, and radiology (according to protocol) but not receive treatment.

The visits should continue at least

meaning that the final clinical follow-up visit

( ) may be scheduled earlier.

